6. TREATMENT OF SUBJECTS

6.1. The Source tool

The Source tool is designed for use in the consultation room. It aims to assist health care providers with giving evidence based information about treatment outcomes by providing visualizations of personalized predictions of treatment outcomes for different treatments of oesophageal and gastric cancer. These predictions result from recently designed and updated prediction models on the survival, toxicity, complications and health related quality of life of oesophageal and gastric cancer patients.

Data:

For survival models data from the nationwide Netherlands cancer registry were used. For the potentially curative and palliative settings, a multivariate Cox regression models were created and validated according to a temporal internal-external scheme (discriminative ability (c-indices): 0.71 for metastatic oesophagogastric cancer and 0.70 for metastatic gastric cancer, and 0.76 for the potentially curative models).⁹

For toxicity and complications of treatments, extensive meta-analysis data were used. For toxicity the literature was searched for prospective phase II or III randomized controlled trials (RCTs) on palliative first-line systemic treatment for advanced esophagogastric cancer. All CTCAE 1–2 (mild) and 3–4 (severe) adverse events from each chemotherapy arm were extracted and pooled by using single-arm meta-analysis.¹⁰ For complications of treatment, databases were searched for randomized controlled trials investigating curative treatment regimens for gastric cancer. All grade 1–2 (mild) and grade 3–5 (severe) adverse events were extracted per cytotoxic regimen and combined in a single-arm random-effects meta-analysis.¹¹

For health related quality of life, data from the national registry on health related quality of life of oesophageal and gastric cancer patients (POCOP) was used to create a mixed-effects model with treatment as a predictor based on 725 potentially curable patients. For metastatic patients, data from a meta-analysis on health related quality of life in the metastatic setting is provided.¹² All models in the Source tool are updated when new, relevant data are available.

Visualizations:

- For survival data, both icon arrays and Kaplan Meier curves are implemented in order to be able to tailor the presentation format to individual patients. Adjustments to the displayed treatments and time period can be done, as well as to the visibility of confidence intervals. In the Kaplan Meier curve there is a possibility of showing three scenarios of survival^{13,14} by shading the areas under the curve.
- For toxicity and complications (labeled as side effects) data, bar colored bar charts for both top 3 and all side effects are available. All treatments and side effects can be displayed separately or can be compared in one display.
- For health related quality of life data, simple line graphs are available for overall quality of life, symptom and functioning scores. Display of time period, confidence interval and general population (reference) scores can be adjusted.
- All visualizations can be joined in a simple overview of the three outcome categories (survival, side-effects, quality of life). An automatically generated text will accompany the graphs to serve as a summary of the communicated treatment outcomes. This overview can be saved as PDF or printed and handed to the patient.

6.2. The Source training

The training aims to teach participants to inform patients about outcomes of treatment. The training is placed in the context of shared decision making (SDM), following the 4-step model by Stiggelbout et al., 2015.⁸

The training is provided in small groups (3-6 participants) by an experienced trainer and supported by professional actors. The training aims to address knowledge, attitude and skills. The learning goals of the training are:

- Knowledge: After the training, the participant knows: (1) the basic theory of information giving (relevance, goal and tips and tricks), (2) the framework of SDM applied to both situations in which there is one preferred option and in which there are more conceivable options, (3) the do's and don'ts when giving risk and benefit information, (4) the functionalities of the Source tool and the data and calculations behind the Source tool.
- Attitude: After the training, the participant is aware of one's goal when informing patients about treatment and treatment outcomes and one's barriers to use evidence-based information about treatment outcomes. The participant has a generally positive attitude towards using evidence based information about treatment outcomes and is willing/motivated to use this information (by using the Source tool) in one's own consultations.
- Skills: After the training, the participant is capable of applying the required (risk) information giving skills in consultations about treatment and treatment outcomes and is able to use evidence-based information when doing so. These two learning goals include: (1) giving evidence-based information in a manner which patients can understand, while not taking away all their hopes, (2) tailoring the amount and content of the information to individual patients' needs, (3) using information giving skills to facilitate patients decision making.

The training includes:

- 1. Access to an e-learning providing theory and tips and tricks
- 2. Two half-day training sessions with instruction, role play and personal feedback
- 3. An individual (or pairwise) booster session of 1 hour
- 4. Access to an online consultation room tool, providing evidence-based information on outcomes of treatment for oesophageal and gastric cancer patients (the Source tool, see 6.1)

7. METHODS

7.1. Study parameters/endpoints

7.1.1. Main study parameters/endpoints

The primary outcome is (numerical) precision of information about outcomes of treatment in the treatment information consultation. To observe this, we will audiotape and content code the consultation, using the SOURCE observational scale, to assess the primary outcome.

7.1.2. Consultation - secondary study parameters/endpoints

- Health care providers' personalization of treatment outcome information (SOURCE observational scale)
- Health care providers' tailoring of treatment outcome information to patients' information need (SOURCE observational scale)
- Health care providers' use of visualizations (SOURCE observational scale)
- Health care providers' setting the agenda (SOURCE observational scale)
- Utterance level: health care providers' use of time frame, initiative for discussing outcomes (health care provider, patient, informal caregiver), treatment outcome category discussed (survival, side-effects, quality of life) (SOURCE observational scale)
- Consultation time

7.1.3. Health care provider - secondary study parameters/endpoints

- Health care providers' satisfaction with communication and decision making (Patient Satisfaction Questionnaire (PSQ-5 doctor version))
- Health care providers' use of the Source tool (observation)
- Health care providers' evaluation of the Source tool (tailor made evaluation questionnaire)
- Health care providers' evaluation of the Source e-learning (tailor made evaluation questionnaire)
- Health care providers' evaluation of the Source face-to-face training (tailor made evaluation questionnaire)
- Health care providers' intention to inform patients about treatment outcomes using numbers (effect training only) (CPD reaction questionnaire)

7.1.4. Patient – secondary study parameters/endpoints

- Patient satisfaction with communication and decision making (Patient Satisfaction Questionnaire (PSQ-5))
- Patients' evaluation and knowledge of the information provided by the health care provider (INFO-25 + tailor made items on information about outcomes of treatment)
- Patient-reported shared decision making (Shared Decision Making Questionnaire (SDMQ-9))
- Patients' evaluation of the decision made (Decisional Conflict Scale (DCS))
- Patients' health related quality of life (EORTC QLQ-C30 + EORTC QLQ-OG25)
- Patients' trust in the health care provider (Trust in the Oncologist Scale (TiOS-sf))
- Patients' anxiety (State-Trait Anxiety Inventory (STAI))
- Patients' helplessness/hopelessness + fighting spirit ((Mini-)Mental Adjustment to Cancer scale ((Mini-)MAC))
- Patients' (provisional) treatment decision (medical record)

7.1.5. Demographical and personal study parameters

Health care providers:

- Age
- Gender

- Nationality
- Level of medical training/ job position
- Specialism
- Earlier communication skills training

Patients:

- Tumour location
- Age
- Gender
- Personal living situation
- Number of children (under 18)
- Nationality
- Educational level
- Perceived efficacy in communication before the consultation
- Information need
- Experience with graphs/numbers

7.2. Study procedures

7.2.1. Patient study procedures

Patients with oesophageal or gastric cancer who are scheduled for a treatment information consultation, will be approached by telephone for informed consent by a SOURCE research employee. Informed consent forms together with the information letter and the baseline TO questionnaire will be sent to the patient by mail or email.

Consenting patients will be asked to fill in a questionnaire at home before the start of the consultation (T0 P; 7-15 minutes) and one in the waiting room, just before the start of the consultation (T1 P; 3-5 minutes).

Together with receiving T1, patients will receive an envelope containing the T2 questionnaire (10-20 minutes). Patients will be asked to fill in the T2 questionnaire within a time period of two weeks after the consultation. The treatment information consultation will be audio recorded. Dependent on the procedures as agreed upon with the participating centers, either the research nurse of the participating center or a researcher of the SOURCE study will facilitate the audiorecording and questionnaire completion.

Three months after the consultation, patients will be asked to fill in the last questionnaire (T3 P; 10-15 minutes). Patients participating in the POCOP trial will not receive this questionnaire. For these patients, the data from the T2 questionnaire will be acquired through the POCOP database.

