shown). The associate or nurse will check whether the family members present have provided consent for audio recording the consultation. The patient will be asked to fill out a two page questionnaire (T1 P). In addition, the patient will receive the post-consultation questionnaire (T2 P) with a return envelope.

4. Audio recording.

Prior to the outpatient clinic appointment, the health care provider will be informed about the fact that the patient is participating in SOURCE and that the consultation will be audio-recorded. Either the research associate, the research nurse or the health care provider will operate the recorder (depending on local agreements). If done by a research nurse or associate, they won't be present during the consultation. Patient and family won't be approached after the consultation. Encrypted audio devices will be used as soon as available to prevent access after the recording has been saved on the device. All audio recordings will as soon after the consultation as possible be filed in a strict protective digital repository.

5. Follow up.

Patients will receive one more follow-up questionnaires at 3 months post- consultation (T3 P). Their medical files will be checked for information about treatment until 12 months post-consultation, either by a research associate or a research nurse.

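### Section 7.2.1 withholds the 3-month T3 form from POCOP participants but names T2 as the form to take from POCOP, leaving their 3-month questionnaire data without a stated source

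*Protocol*

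**What the plan says.** Protocol section 7.2.1 sets out the patient questionnaires in order. T2 comes after the consultation: "Patients will be asked to fill in the T2 questionnaire within a time period of two weeks after the consultation". It is given to the patient in an envelope together with T1. T3 is the last form and is due three months after the consultation.

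Two sentences on POCOP follow directly after T3 is introduced. The first is an exemption: "Patients participating in the POCOP trial will not receive this questionnaire". The second names a replacement source: "For these patients, the data from the T2 questionnaire will be acquired through the POCOP database".

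Section 10.1.3 describes the same procedures for patients in the trial. On T2, in the waiting room, it says: "In addition, the patient will receive the post-consultation questionnaire (T2 P) with a return envelope". On follow-up it again has patients receiving a questionnaire (T3 P) at three months. It mentions POCOP in neither place. It also provides for follow-up that needs no questionnaire: "Their medical files will be checked for information about treatment until 12 months post-consultation".

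The only description of what POCOP contains is in section 6.1, on the data behind the tool, where it is a national registry on health related quality of life. Section 7.2.1 calls it a trial.

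**The concern.** The POCOP rule in 7.2.1 is an operational instruction. It tells staff which patients not to send a form to and where to get the data instead. The form it withholds is T3, and the form it says to retrieve is T2. Followed literally, it has staff request from POCOP something the study already collects by hand, and leaves nobody responsible for obtaining the 3-month data.

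Section 10.1.3 can be read as sending T3 to everyone. Staff working from that section would post the form to POCOP participants, and staff working from 7.2.1 would not.

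At stake are the patient-reported secondary outcomes measured at three months, for an identifiable subgroup. Questionnaire answers that nobody requests at three months cannot be recovered later, so the text should be settled in the protocol and not left to the analysis stage.

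**Working it through.** No figure in the protocol depends on this point, so the check sets the passages side by side.

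| Item | T2 (patient) | T3 (patient) |
|---|---|---|
| When completed (7.2.1) | Within two weeks after the consultation | Three months after the consultation |
| How delivered | In an envelope with T1 (7.2.1); handed over in the waiting room (10.1.3) | Three months later, as the last form (7.2.1); as one more follow-up form (10.1.3) |
| Withheld from POCOP participants (7.2.1) | No | Yes |
| Taken from the POCOP database (7.2.1) | Yes | Not stated |
| POCOP exception in 10.1.3 | None | None |

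1. **Which form is withheld.** The exemption refers back to the form named in the sentence before it: "Three months after the consultation, patients will be asked to fill in the last questionnaire (T3 P; 10-15 minutes". That form can only be T3.

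2. **Which form is retrieved.** The next sentence names T2. T2 needs no substitute, because both 7.2.1 and 10.1.3 give it directly to the patient and neither excludes POCOP participants.

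3. **What is left for T3.** Neither section, nor any other part of the protocol, gives a source for POCOP participants' T3 data. The table row for retrieval is filled for the form already in hand and empty for the form withheld.

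4. **Whether 10.1.3 resolves it.** It does not. Its follow-up item reads: "Patients will receive one more follow-up questionnaires at 3 months post- consultation (T3 P". With no exception attached, it differs from 7.2.1 on whether POCOP participants get the form at all.

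5. **Whether POCOP could supply T3.** The protocol describes its content only as "data from the national registry on health related quality of life of oesophageal and gastric cancer patients (POCOP". Section 7.1.4 lists the patient instruments, which go beyond quality of life (satisfaction, information, shared decision making, decisional conflict, trust, anxiety and adjustment to cancer), but does not assign them to T0, T1, T2 or T3. The protocol therefore neither shows that POCOP covers T3 nor shows that it does not. Nor does it say that POCOP's measurements fall at about three months after this study's consultation.

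6. **What is outside the problem.** The primary outcome is coded from audio recordings (7.1.1 and 9.1). The treatment information comes from medical files up to 12 months (10.1.3). Neither depends on T3.

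7. **Size.** The number affected is the number of trial patients who are also in POCOP. The protocol does not give this number, or any figure from which to derive it.

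**The case against.** The strongest reply is that this is a slip of one character. The sentence on the POCOP database has an obvious purpose, which is to say where the data of the withheld form come from. Read for that purpose, T2 should be T3 and the paragraph makes sense. Likewise, 10.1.3 states the general procedure and 7.2.1 a specific exception, so the omission in 10.1.3 is a matter of harmonisation. Most of this stands: T2 is most likely an error for T3. It does not remove the point, because the sentence governs data collection and the document does not correct itself elsewhere.

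A reader might infer more than the text supports, in four ways:

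- **That T2 data are lost or come from an unsuitable source.** T2 is handed to every patient, so it is collected directly whatever the sentence says.
- **That POCOP patients have no 3-month data at all.** Only questionnaire data are in question, since treatment information is taken from medical files. Even the questionnaire data are missing only if the wording is applied literally and nothing is retrieved from POCOP for month 3.
- **That the loss of precision can be calculated.** Any such figure would need an assumed POCOP share and the further assumption that POCOP supplies nothing at three months. The first is not stated, and the second runs against the evident purpose of the sentence.
- **That the missing data would bias the comparison, or that T3 certainly contains items POCOP lacks.** Nothing in the protocol says that POCOP participation differs between control and intervention phases or between centres. The content of T3 is not given, and using a quality-of-life registry in its place is equally compatible with T3 being mainly a quality-of-life form.

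**Conclusion.** The inconsistency is real and is in the current text. Section 7.2.1 withholds one form and names another for retrieval, so the source of POCOP participants' 3-month questionnaire data is not stated. Section 10.1.3 does not carry the exemption. The most likely explanation is a labelling error, not a deliberate choice.

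The consequence is confined to patient-reported secondary outcomes at three months among POCOP participants. Its extent cannot be quantified from the protocol. The conclusion rests on reading the exemption as referring to T3, which the order of the sentences leaves in no real doubt. Whether POCOP can fully replace T3 is an open question for the sponsor, not an established failure. The correction is worth making because it costs almost nothing and the data cannot be collected afterwards.

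**What to change.** 1. The sponsor confirms which form was meant. If it was T3, change T2 to T3 in the POCOP sentence of 7.2.1.
2. Add the same POCOP exception to the follow-up item of 10.1.3, so that both sections give staff one rule.
3. Confirm that POCOP holds the T3 measures for these patients at about three months after the consultation. The protocol currently describes it only as a quality-of-life registry.
4. If any T3 item turns out not to be held there, ask POCOP participants for that item directly. If POCOP covers all of T3, no extra form is needed.

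The cost is a wording amendment in two sections and a check of POCOP's content and timing. Additional patient burden arises only if step 3 finds a gap, and then only for the missing items. The design, the sample size and the primary analysis are unchanged.

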7.2.2. Health care provider study procedures

Patient inclusion

After informed consent is signed by the health care provider, each consultation with a participating patient will be recorded on audio. After the consultation, health care providers will fill in a short questionnaire (T2 HCP; 1-2 minutes) on their evaluation of the consultation. Health care providers' use of Source tool, will be logged. Each action will be logged and labeled by

moment in time. Entered patient data and health care providers' study code will be stored using 512-bit RSA encryption.

Simulated patient assessment 1 (before intervention)

During the control measurement period (see Figure 2), the first simulated patient assessment (SPA) will take place, which will be recorded on audio. At the first SPA, health care providers will be asked to fill in T1 HCP (3-5 minutes). After the consultation, health care providers will also fill in T2 HCP.

Transition period

After completion of the e-learning, health care providers will be asked to fill in a short evaluation questionnaire on the e-learning (T3 HCP; 5-10 minutes).

Simulated patient assessment 2 (after intervention)

After training is completed, the second SPA will take place. At the second simulated patient assessment, health care providers will fill in T4 HCP (5-10 minutes) and T2 HCP.

End of study

Lastly, at completion of their patient inclusion, health care providers will fill in a short evaluation of the tool (T5 HCP; 5-10 minutes).

7.3. Withdrawal of individual subjects

Subjects can leave the study at any time for any reason if they wish to do so without any consequences. The investigator can decide to withdraw a subject from the study for urgent medical reasons.

7.4. Replacement of individual subjects after withdrawal

Participating patients will only be replaced after withdrawal if the minimum of 126 audio recoded consultations in total or the minimum of 2 control measurements and 2 interventions measurements per health care provider is not reached.

Participating health care providers that did not succeed in including 2 control measurements and 2 interventions measurements will only be replaced if the minimum of 21 in total is not reached. Health care providers who withdraw during the study will only be replaced if they drop out after informed consent, but before training.

7.5. Premature termination of the study

Not applicable, as we do not expect the study to be terminated prematurely due to proven unsafety.

8. SAFETY REPORTING

The investigator will inform the subjects if anything occurs, on the basis of which it appears that the disadvantages of participation may be significantly greater than was foreseen in the research

proposal. Safety of the participants will be reconsidered and if considered insufficient, the study will be suspended. The investigator will take care that all subjects are kept informed.

9. STATISTICAL ANALYSIS

9.1. Primary study parameter

Audio tapes of consultations will be analyzed, using Noldus' The Observer XT software, on the primary outcome. Time-based analysis on all utterances of information on treatment outcomes is performed. Each utterance will receive a code based on the study specific coding scheme. Utterance scores will be summarized on the level of the consultation and compared between control and intervention measurements in a within-subjects analysis. Effects with one-sided p-values < .05 will be considered significant; 95Cl's as well as effect sizes will be provided. Baseline differences across the compared patient groups on socio-demographic (age, gender, educational level, etc.) and clinical characteristics (cancer phase at time of the consultation, time since diagnosis, etc.) as well as patients' baseline measures will be examined with the appropriate statistical tests (ANOVA, Chi-squared tests). All analyses of effectiveness will be controlled for specialization of the health care provider, profession of the health care provider (specialist, fellow, nurse specialist, physician assistant) and center specific characteristics (academical or peripheral hospital, starting time of intervention).

Reasons for missing data will be registered and recorded. Dependent on the type of missing data, the appropriate procedures will be used. If necessary, multiple imputation could be applied.

